22. **Blood for PF-05082566 Pharmacokinetics:** Blood samples will be collected during Cycle 1-4 on (a) Day 1 at pre-dose and end of infusion; (b) During Cycle 5 on Day 1 at pre-dose, end of infusion, and at 2, 6, and 24 hrs after the start of infusion; (c) on Days 8 (192 hours), and 15 (360 hours) after start of infusion (See [Section 7.2](#) for guidelines on timing of blood draws); (d) During Cycle 6 on Day 1 at pre-dose; (e) During Cycle 7 on Day 1 at pre-dose, end of infusion, 24 hrs after the start of infusion and on Day 8; and (f) Beyond Cycle 7, PK samples will be collected at pre-dose, for every 2 cycles up to Cycle 12, every 4 cycles thereafter, and at the End of Treatment visit. **For patients in expansion cohorts**, same PK schedule will be followed for at least 10 patients in total from all expansion cohorts. For other patients (all expansion cohorts), predose samples on Day 1 will be collected for Cycles 1, 3, 5, 6 ([Section 7.2.1](#)) and 7. Beyond Cycle 7, PK samples will be collected at pre-dose, for every 2 cycles up to Cycle 12, and every 4 cycles thereafter. Timing of sampling may be modified based on emerging PK data. For patients discontinuing from the study, a PK sample should be collected at the End of Treatment assessment.
23. **Blood for MK-3475 Pharmacokinetics:** Blood samples will be collected (a) During Cycle 1- 4 on Day 1 at pre-dose and end of infusion; (b) During Cycle 5 on Day 1 at pre-dose; and end of infusion; (c) During Cycle 7 on Day 1 at pre-dose, end of infusion, 24 hrs, and on Day 8 (192 hrs) after start of infusion (See [Section 7.2](#) for guidelines on timing of blood draws). Beyond Cycle 7, PK samples will be collected at pre-dose every two cycles up to cycle 12, and every 4 cycles thereafter. Additionally, PK samples will be collected at 28 days, 3 months, and 6 months after the end of MK-3475 treatment. **For patients in an expansion cohort**, the same PK schedule will be followed for at least 10 patients in total from all expansion cohorts. For other patients (all expansion cohorts), predose samples on Day 1 will be collected for Cycles 1, 3, 5 and 7. Beyond Cycle 7, PK samples will be collected at pre-dose (Day 1), every 2 cycles up to Cycle 12, and every 4 cycles thereafter. Timing of sampling may be modified based on emerging PK data. For patients withdrawing from the study, a PK sample should be collected at the End of Treatment assessment.
24. **CCI**

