5.3.1. PF-05082566

PF-05082566 will be administered intravenously (IV), q3wks on Day 1 of each cycle.

PF-0508256 will be administered as a 1 hour infusion. The infusion rate should be reduced or interrupted in the case of symptoms of infusion reaction, and symptomatic treatment administered. The infusion may be continued at one-half the previous rate upon improvement of symptoms. If symptoms persist or worsen, the infusion should be discontinued.

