7.2. Pharmacokinetics Assessments (Dose Escalation and Dose Expansion Cohorts)

PK samples will be assayed for PF-05082566, and MK-3475 using a validated analytical method in compliance with Pfizer (PF-05082566) or Merck (MK-3475) standard operating procedures. Details regarding the collection, processing, storage and shipping of the blood samples will be provided in the study manual.

CCI

All efforts will be made to obtain the pharmacokinetic samples at the scheduled nominal time relative to dosing. However, samples obtained within 10% of the nominal time (eg, within 6 minutes of a 60 minute sample) will be considered protocol compliant, and the exact time of the sample collection noted on the CRF. If a scheduled blood sample collection cannot be completed for any reason, the missed sample time may be re-scheduled with agreement of clinical investigators, patient and Sponsor.

In addition to samples collected at the scheduled times, an additional blood sample should be collected from patients experiencing unexpected and/or serious AE's and the date and time documented in the CRF.

As part of understanding the pharmacokinetics of the study drug, samples may be used for evaluation of the bioanalytical method. This additional characterization will be used for internal exploratory purposes and will not be included in the clinical report. Samples collected for this purpose will be retained in accordance to local regulations and if not used within this timeframe, will be destroyed.

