7.2.1. PF-05082566

Blood samples will be collected for PK of PF-05082566 at the following time points:

- During Cycle 1-4 on (a) Day 1 at pre-dose and end of infusion;
- During Cycle 5 on (b) Day 1 at pre-dose, end of infusion, and at 2, 6 and 24 hr post start of infusion; (c) on Days 8 (192 hours) and 15 (360 hours) after start of infusion (See [Section 7.2](#) above for guidelines on timing of blood draws);

- During Cycle 6 on (d) Day 1 at pre-dose only;
- During Cycle 7 on (e) Day 1 at pre-dose, end of infusion, 24 hrs post start of infusion and on Day 8.

Beyond Cycle 7, PK samples will be collected at pre-dose, every two cycles up to Cycle 12, every 4 cycles thereafter, and at the End of Treatment visit.

For patients in expansion cohorts: The same PK schedule will be followed for at least 10 patients in total from all expansion cohorts. For other patients (in all expansion cohorts), predose samples on Day 1 will be collected for Cycles 1, 3, 5, 6 and 7. Beyond Cycle 7, PK samples will be collected at pre dose (Day 1), for every 2 cycles up to Cycle 12, and every 4 cycles thereafter. Timing of sampling may be modified based on emerging PK data. For patients discontinuing from the study, a PK sample should be collected at the End of Treatment assessment day.

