7.2.2. MK-3475

Blood samples will be collected for PK of MK-3475 at the following time points:

- During Cycle 1- 4 on (a) Day 1 at pre-dose and end of infusion;
- During Cycle 5 on (b) Day 1 at pre-dose and end of infusion;
- During Cycle 7 on (c) Day 1 at pre-dose, end of infusion, 24 hrs, and on Day 8 (192 hours) post start of infusion (See [Section 7.2](#) for guidelines on timing of blood draws).

Beyond Cycle 7, PK samples will be collected at pre-dose, every two cycles up to Cycle 12, and every 4 cycles thereafter. Additionally, PK samples will be collected at 28 days after end of MK-3475 treatment (during the End of Treatment visit) and during follow-up at 3 months and 6 months after the end of MK-3475 treatment.

For patients in expansion cohorts: The same PK schedule will be followed for at least 10 patients in total from all expansion cohorts. For other patients (in all expansion cohorts), predose samples on Day 1 will be collected for Cycles 1, 3, 5 and 7. Beyond Cycle 7, PK samples will be collected at pre dose (Day 1), for every 2 cycles up to Cycle 12, and every 4 cycles thereafter. Additionally, PK samples will be collected at 28 days after end of MK-3475 treatment (during the End of Treatment visit) and during follow-up at 3 months and 6 months after the end of MK-3475 treatment.

For patients ending from the study, PK samples should be collected at the End of Treatment assessment day. PK sampling schedule may be modified based on emerging PK data.

CCI

[REDACTED]

[REDACTED]

[REDACTED]

[REDACTED]

[REDACTED]

I [REDACTED]

I [REDACTED]

[REDACTED]

[REDACTED]

[REDACTED]

CCI

[REDACTED]

[REDACTED]

I [REDACTED]

I [REDACTED]

[REDACTED]

[REDACTED]

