### **5.3.1.2. Pharmacokinetic Parameters**

Whether actual or nominal PK sampling time will be used for the derivation of PK parameters will be determined by the results of interim PK analyses. If a PK parameter cannot be derived from a patient's concentration data, the parameter will be coded as NC (ie, not calculated). NC values will not be generated beyond the day that a patient discontinues.

In summary tables, statistics will be calculated by setting NC values to missing. Statistics will not be presented for a particular treatment if more than 50% of the data are NC. For statistical analyses (ie, analysis of variance), PK parameters coded as NC will also be set to missing.

If an individual patient has a known biased estimate of a PK parameter (due for example to a deviation from the assigned dose level), this will be footnoted in summary tables and will not be included in the calculation of summary statistics or statistical analyses.

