#### 6.5.3.4. Dose Delays

Delays will be derived based on study drug administration date and will be grouped into the following categories based on the deviation of the actual to the planned treatment administration day (relative to the previous treatment administration date):

- No delay (including 1-2 days delays).
- 3-6 days delay.
- 7 or more days delay.

For example, for PF-05082566, administered on a 3-week schedule, if one patient receives PF-05082566 on Day 1, then the next PF-05082566 administration date will be on Day 22; however, if the patient receives PF-05082566 at Day 23 or 24, this is considered as 'no delay'.

Number and percentage of patients with delayed study drug administration and maximum length of delay, ie, the worst case of delay if patients have multiple dose delays will be summarized.

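### The Day 8 and Day 15 PK samples carry hour labels 24 h too late (192 h and 360 h instead of 168 h and 336 h), and the SAP leaves open whether nominal times will be used to derive PK parameters

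*Protocol*

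**What the plan says.** The labels appear in four places in the protocol.

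- PF-05082566, Cycle 5: footnote 22 of the Schedule of Activities has "on Days 8 (192 hours), and 15 (360 hours) after start of infusion", and Section 7.2.1 repeats it as "on Days 8 (192 hours) and 15 (360 hours) after start of infusion".
- MK-3475, Cycle 7: footnote 23 has "on Day 8 (192 hrs) after start of infusion", and Section 7.2.2 has "on Day 8 (192 hours) post start of infusion". This drug has no Day 15 sample.

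The day count is fixed elsewhere. Protocol 5.3.1 states "PF-05082566 will be administered intravenously (IV), q3wks on Day 1 of each cycle", and 5.3.2 puts MK-3475 on the same day. SAP 6.5.3.4 confirms the numbering: "if one patient receives PF-05082566 on Day 1, then the next PF-05082566 administration date will be on Day 22".

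On timing tolerance, protocol 7.2 treats "samples obtained within 10% of the nominal time" as compliant and has the exact collection time entered on the CRF. Table 3 gives a window of ±2 days for Cycles 1 to 7.

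On analysis, SAP 5.3.1.2 makes the time base depend on what the interim PK work shows: "Whether actual or nominal PK sampling time will be used for the derivation of PK parameters will be determined by the results". SAP Table 2 derives AUC by the linear/log trapezoidal rule, CL as dose over AUCtau, and half-life by log-linear regression on points judged to be terminal.

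**The concern.** One sample is given two times that differ by 24 h. A site that works from the visit day draws at about 168 h; a site that works from the hours draws at about 192 h. Both can reasonably believe that they followed the protocol.

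The mismatch would do little harm if parameters were always computed from recorded times. The SAP does not commit to that, and it makes the choice depend on results already seen. If nominal times are chosen, concentrations drawn at 168 h and 336 h are placed 24 h too late on the time axis. That error has one direction, so averaging over patients does not remove it. It would carry into the PF-05082566 exposure summaries and into the comparison of steady-state PK with historical data, which is the plan's check for a drug interaction (protocol 3.1 and 9.5.1.1).

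Tables and median plots of concentration use nominal time whatever is decided for the parameters (protocol 9.5.1.1, SAP 6.2.3), so they would show such samples one day late.

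**Working it through.** **Elapsed time.** With dosing on Day 1, elapsed hours = (study day − 1) × 24.

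- Day 8: 7 × 24 = 168 h. Day 15: 14 × 24 = 336 h. Day 22 (next dose): 21 × 24 = 504 h.
- The printed values come back only as 8 × 24 = 192 and 15 × 24 = 360, that is, with dosing on a Day 0 that the plan does not have.
- 192/24 + 1 = Day 9 and 360/24 + 1 = Day 16.

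**The 10% rule (protocol 7.2).**

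- Around 192 h: 172.8 to 211.2 h. A draw at exactly 168 h is outside, being 24/192 = 12.5% early.
- Around 360 h: 324 to 396 h. A draw at 336 h is inside.

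**Effect on AUCtau and CL.** Inputs: half-life 10 days (protocol 1.2.8), so k = ln 2/240 h; 1-hour infusion at steady state with one-compartment decline (my assumption); samples at pre-dose, 1, 2, 6, 24, 168, 336 and 504 h, the last being the Cycle 6 pre-dose sample; the SAP's trapezoidal rule. The 168 h and 336 h concentrations are then analysed at 192 h and 360 h.

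For a mono-exponential decline, the log trapezoid over a segment equals (C1 − C2)/k × (nominal length/true length). Set the end-of-infusion concentration to 1. The concentrations at 24, 168, 336 and 504 h are then 0.9357, 0.6174, 0.3800 and 0.2339. In units of 1/k:

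| Segment (true h) | Area | Nominal/true length | Change |
|---|---|---|---|
| 0 to 1 | 0.0018 | 1/1 | 0 |
| 1 to 24 | 0.0643 | 23/23 | 0 |
| 24 to 168 | 0.3184 | 168/144 | +0.0531 |
| 168 to 336 | 0.2373 | 168/168 | 0 |
| 336 to 504 | 0.1461 | 144/168 | −0.0209 |
| Total | 0.7679 | | +0.0322 |

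AUCtau: 0.0322/0.7679 = +4.2%. CL: 1/1.042 − 1 = −4.0%.

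Over an assumed range of half-lives from 5 to 21 days, AUCtau moves by +7.3% to +2.1% and CL by −6.8% to −2.0%. Bi-exponential profiles with an assumed 24 h distribution phase and a 10-day terminal phase give AUCtau +4.6% to +5.5%.

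**Effect on half-life.** True value 10.0 days, same one-compartment data:

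| Points fitted | Half-life (days) |
|---|---|
| Days 15, 22 | 8.6 |
| Days 8, 15, 22 | 9.3 |
| Days 8, 15 | 10.0 |
| 24 h, Days 8, 15, 22 | 10.0 |
| 24 h, Days 8, 15 | 10.8 |

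The first row is 10 × 144/168. Days 8 and 15 alone show no change because both points shift by the same 24 h.

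**Draws at the printed hours.** With samples taken at 192 h and 360 h and analysed at those times, the change in AUCtau, CL and half-life is zero.

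**The case against.** The label error itself cannot be argued away. The case on the other side concerns consequence and scope.

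- **Two conditions are needed.** Parameters are biased only if the SAP choice falls on nominal time and samples are drawn earlier than the hour label. A site that follows the hours draws on Day 9 or Day 16, inside the ±2-day window, and adds no bias. Section 7.2 also tells sites to aim for the nominal time. This stands, and it makes the bias conditional.
- **Compliance is affected at one point only.** The Day 15 draw is compliant, and a Day 8 draw taken 4.8 h later in the day than the dose (172.8 − 168) is too. This stands.
- **The SAP has safeguards.** Section 5.3.1.2 keeps parameter estimates known to be biased out of the summaries, and 5.3.1.1 sets concentrations with worrying timing deviations to missing in summary tables and median plots. They help in part. An error built into the nominal time may not be recognised as a deviation, and a correctly timed Day 8 sample could be the one flagged.
- **Scope is narrow.** MK-3475 has one such label, and protocol 9.5.1.1 assigns its parameters to a population PK model, although SAP Table 2 names both drugs. PK is a secondary endpoint and no formal hypothesis test is planned. This stands.

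A reader might infer two stronger things. One is that AUC, CL and half-life are all biased. SAP Table 2 leaves the terminal points to judgement and derives half-life only if data permit, so no direction can be claimed for it. The other is that the visit window turns 4% into a much larger error. Draws two days early (120 h and 288 h) analysed at the printed hours do give AUCtau +13%, but with the labels corrected to 168 h and 336 h the same draws still give +8.9%. Most of that error comes from the window and from nominal-time analysis. Draws two days late under the present labels give −4.0%, the opposite sign. Nor do the 120 h and 288 h draws meet the 10% rule, being 37.5% and 20% early.

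**Conclusion.** The point holds in a limited form. The day and hour labels for the Day 8 and Day 15 samples contradict each other by 24 h under the plan's own day count, and the SAP does not commit to actual sampling times.

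The realistic size is about +4% on AUCtau and −4% on CL for PF-05082566 in Cycle 5. It rests on a 10-day half-life, one-compartment decline, draws at 168 h and 336 h, and nominal-time analysis. The documents do not show that a shift of this size would change a conclusion. No general statement about half-life is supported.

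The correction is still worth making: the error is plain, the choice of time base should not wait for interim results, and the exact times are already recorded.

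**What to change.** 1. Reconcile day and hour in footnotes 22 and 23 of the Schedule of Activities and in protocol Sections 7.2.1 and 7.2.2. If the Day 8 and Day 15 visits are kept, the labels become 168 h and 336 h. If the hours are kept, the visits become Days 9 and 16.
2. Replace the sentence in SAP 5.3.1.2 on the choice of sampling time with: *Actual elapsed sampling times will be used to derive all non-compartmental PK parameters; nominal times will be used only for tabulating and plotting concentrations.*

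Both are wording changes. They need no new data or samples. The second removes the parameter bias even for samples already drawn under the present labels.

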25. CCI [REDACTED]
26. **Banked Biospecimen (blood):** A 4-mL blood biospecimen will be collected on Day 1 Cycle 1 (**pre-dose**) to be retained for potential pharmacogenomic/biomarker analyses related to drug response, unless prohibited by local regulations or ethics committee decision.
27. **Blood for Pharmacogenomics (RNA):** Blood samples will be collected during Cycle 1 Day 1 (pre-dose) and Cycle 2 Day 1 (pre-dose).
28. **Blood for T cell Receptor Quantitation:** Blood sample taken pre-dose on Day 1 of Cycles 1 through 5, and at End of Treatment.
29. **Blood for PF-05082566 Immunogenicity (ADA) Testing:** Blood for PF-05082566 immunogenicity testing will be collected at pre-dose (Day 1), Cycles 1, 3, 5, 7, and subsequently pre-dose (Day 1) every 2 cycles up to Cycle 12, and every 4 cycles thereafter. For patients discontinuing study drug treatment, immunogenicity samples should be collected at the End of Treatment assessment day. If ADAs are detected, additional samples may be collected approximately every 3 months (coinciding with disease assessment visit) until ADA levels return to baseline.
30. **Blood for MK-3475 Immunogenicity (ADA) Testing:** Blood for MK-3475 immunogenicity testing will be collected at pre-dose in Cycles 1,3, 5, 7 and subsequently predose every 2 cycles up to Cycle 12 and every 4 cycles thereafter. Additionally, ADA samples will be collected at 28 days, and during Follow-Up (3 months and 6 months after the end of MK-3475 treatment).
31. **End of Treatment:** To be performed approximately 28 days after the last dose of study drug. Obtain these assessments if not completed during the previous week on study (during the previous 6 weeks on study for tumor assessments).
32. **Follow Up:** Patients should be evaluated up to 90 days after last dose of study treatment. Refer to the protocol for specific guidelines. Patients continuing to experience toxicity following discontinuation of study treatment will continue to be followed at least every 4 weeks until resolution or determination, in the clinical judgment of the Investigator, that no further improvement is expected. PK and immunogenicity samples should be collected as described in the PK and Immunogenicity Assessment section in Schedule of Activities ([Table 3](#)). Patients whose disease has not progressed at the end of treatment will enter into disease follow-up. During this follow-up period, patients will have disease assessments performed every 12 weeks \pm 7-days. Once patients have exhibited disease progression or began a new anti-cancer therapy, or 6-month follow-up from the date of the first dose of the last enrolled patient, whichever occurs first, they will be withdrawn from the study. See [Section 4.3.1](#) Contraception for guidelines on contraception checks during this period.
33. **De novo tumor biopsy for biomarker assessment (Dose escalation):** For patients in dose-escalation cohorts, unscheduled optional de novo tumor biopsies may be collected at the discretion of the investigator and sponsor to support the assessment of disease progression.
34. **De novo tumor biopsy for biomarker assessment (Expansion cohorts):** Mandatory for patients in expansion cohorts only. A de novo biopsy will be required at study entry followed by a second biopsy at the time of the Week 9 scans (after 3 cycles of treatment).
35. **Continued Treatment Beyond Cycle 8:** This will be on a reduced visit schedule (Day 1 of each cycle), or as clinically indicated.
36. **Thyroid Function Tests:** To be collected every 2 cycles for the first 8 cycles, and then every 4 cycles (Cycles 1, 3, 5, 7, 11, 15 etc.).
37. **Hepatitis B and C Tests:** Conduct tests for hepatitis B surface antigen, core antibody, and anti-hepatitis C. Other tests may be conducted per standard practice to confirm an active hepatitis infection.

Table 4. Required Laboratory Tests

SAFETY LABORATORY REQUIREMENTS	
Refer to the Schedule of Activities table for specific timepoints and instructions	
Assessments	
Hematology Panel:	Chemistry Panel:
Absolute Neutrophil Count	Sodium
Hemoglobin	Potassium
	Total Calcium
Platelet Count	Creatinine
WBC with differential (5-part if available)	Albumin
	Alanine aminotransferase (ALT)
	Aspartate aminotransferase (AST)
	Glucose
	Phosphorus
	Magnesium
	Total Bilirubin***
	Blood urea nitrogen (BUN)
	Alkaline phosphatase
	Lactate dehydrogenase (LDH)
	Immunoglobulin G
	Total protein
	Uric acid (or urate)
Coagulation Panel: international normalized ratio (INR) or prothrombin time (PT), Partial thromboplastin time (PTT)	Thyroid function assessments: T3, FT4 and TSH. In the presence of clinical suspicion of hypopituitarism or hypoadrenalism, laboratory testing should include one or more of the following: ACTH, and cortisol levels before and 30-60 minutes after corticotrophin stimulation.
Urinalysis: measurement of pH, specific gravity, protein/albumin, glucose, blood/hemoglobin, ketones/acetone. Urine dipstick for urine protein: if positive collect 24-hr and microscopic (Reflex Testing), Urine dipstick for urine blood: if positive collect a microscopic (Reflex Testing). Pregnancy Test (serum or urine): Conducted for women of childbearing potential only.	Hepatitis B and C tests: Conduct tests for hepatitis B surface antigen, core antibody, and anti-hepatitis C. Other tests may be conducted per standard practice to confirm an active hepatitis infection.
*** For potential Hy's Law cases, in addition to repeating AST and ALT, laboratory tests should include albumin, creatine kinase, total bilirubin, direct and indirect bilirubin, gamma glutamyl transferase, prothrombin time (PT)/INR, alkaline phosphatase, and acetaminophen levels.	

TABLE OF CONTENTS

LIST OF TABLES	28
LIST OF FIGURES	28
APPENDICES	29
1. INTRODUCTION	30
1.1. Indication.....	30
1.2. Background and Rationale	30
1.2.1. Scientific Rationale: 4-1BB Target Biology and Mechanism of Action.....	30
1.2.2. Pre-clinical Development of PF-05082566	31
1.2.2.1. In Vitro PF-05082566 Data	31
1.2.3. In Vivo Data: Functional Activity of PF-05082566.....	32
1.2.3.1. Anti-tumor Activity of PF-05082566.....	33
1.2.4. Combination Studies.....	33
1.2.5. Pre-Clinical Pharmacokinetics of PF-05082566	34
1.2.6. Pharmacokinetics CCI Relationship of PF-05082566.....	34
1.2.7. Preclinical Toxicology of PF-05082566.....	35
1.2.8. Clinical Safety of PF-05082566	35
1.2.9. MK-3475.....	36
1.2.9.1. Clinical Safety and Efficacy of MK-3475	38
1.2.9.2. MK-3475 Clinical Efficacy	38
1.3. Starting Dose Selection Strategy	39
2. STUDY OBJECTIVES AND ENDPOINTS.....	41
2.1. Objectives.....	41
2.2. Endpoints.....	41
3. STUDY DESIGN.....	42
3.1. Study Overview	42
